Online comprehensive health questionnaire (CHQ) or update of previous health questionnaire		X			
Blood draw for clinical function blood tests (liver, kidney, thyroid); review for eligibility and return results to individuals		X			X
Anthropometry (weight, height, waist circumference)		X		X	X
Blood draw for serum POPs concentrations		X		X	X
Analyses of serum POPs concentrations (baseline, 3 mo., 6 mo.)	After all samples collected				
Randomization			X		
Dietary Assessments			X	X	X
Physical activity assessments			X	X	X
Pill count to check adherence			Months 3, 6		
Compensation			\$40	\$60	
Initiate a weekly telephone call – to answer questions, encourage adherence and determine any adverse events or new health problems – then reduce frequency of calls depending on each patient's needs and preference.			Months 1 -6		
Medication dispensed (Orlistat or placebo)			Enrollment: 3 mo. supply Month 3: 3 mo. supply		
Multivitamins dispensed (200ct)			X		
Post-study follow-up telephone calls			One week and one month after completion		

Study Design Overview: A randomized, double-blind, placebo-controlled 6-month trial will be conducted among selected participants from the PBB Registry. Signed informed consent will be obtained, in person or online, after discussion with study staff and an opportunity to ask questions. Potential participants will be screened for eligibility by self-report of health information and clinical laboratory tests. Study participants will be randomized into one of two groups: the Orlistat (intervention) group or the control (placebo) group. Both groups will be prescribed the same diet and exercise regimen.

Anthropometry measurements (weight, height, waist circumference) will be obtained at enrollment and serum levels of PBB, PCB, DDT/DDE and PBDE (POPs) will be measured at enrollment, at 3 months and at 6 months (all chemical analyses will be done at the conclusion of the trial). We will determine if body weight and serum concentrations of POPs have changed over time in each group. Subgroup analyses by amount of weight loss, enrollment PBB concentration, and gender will be undertaken as well. Data will be analyzed to see if the Orlistat group experiences greater weight loss than placebo and secondarily, whether the Orlistat group experiences a greater reduction in serum POPs over the course of the trial.

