data can be reported in a variety of formats and exported to a file for statistical analysis. Of particular interest in this study are dietary intake of total energy, macronutrients and selected food groups (e.g., fruits, vegetables, high-fat snacks). A potential limitation is inaccurate reporting of dietary intake; however, [name] has extensive experience in the collection of dietary data and in maximizing the accuracy of this process.

4. Physical activity

We will assess recent usual physical activity and inactivity using the validated form of the Women's Health Initiative Physical Activity Questionnaire (WHI-PAQ) [14, 15] which assesses physical activity for men as well as women, across several domains (leisure, domestic and yard, work and transportation-related activities) and when scored can provide both continuous and categorical indicators of overall activity. This will be measured at enrollment, 3, and 6 month intervals.

Blinding: Due to their roles in assignment of participants to Orlistat or Placebo groups, and dispensing the appropriate medications, [name] and [name], R.Ph and will not be blinded. All other study staff will be blinded to patient medication assignment to ensure no bias occurs in patient data collection and reporting. This will be maintained through the secure database given access only to those unblinded. All other laboratory and study staff, including the PI will remain blinded. [name] will be notified of adverse effects reported and will be unblinded whenever necessary for patient safety. More information is provided in the Data Safety Monitoring Plan.

Risks to Human Subjects

a. Potential risks:

Potential risks associated with the use of Orlistat include:

- Headache
- Oily rectal discharge
- Urgent need to have a bowel movement
- Inability to control bowel movements
- Oxalate kidney stones/oxalate kidney damage
- Pancreatitis
- Liver injury or failure

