Individuals eligible for the study will be recruited from among those who have participated in PBB observational research. All Registry members that meet the provisional eligibility criteria will be contacted and informed about the trial by mail and telephone. The call will include detailed information about the trial procedures and potential risks of participating. If the individual indicates interest in participating, verbal consent will be obtained and the participant will be instructed to sign the online consent form.

b. Protections Against Risk

All study participant data will be organized and maintained by an assigned study ID number. The results will be published only in aggregate form. All identifying information will be kept in locked cabinets and secure computer files and will only be used by select study personnel for purposes of contacting cohort members, data cleaning and analysis when necessary. Identifying information in electronic form will be kept on a password protected research drive in a folder that is only accessible to the study personnel who need this information. RSPH aligns with the National Institute of Standards and Technology (NIST) special publications (800 series) for identifying, assessing, and managing information security risk within a technology environment. Drawing on federal and industry best practices, RSPH has implemented a series of multi-layered security controls to protect the integrity, reliability, and confidentiality of data. Additional protections

- Venipuncture will be conducted by trained phlebotomists.
- Study participants will report their health status weekly in the first few months and then monthly to the research team via phone. Additionally, participants will be informed to contact the research team in the case of changes in medical status or occurrence of side effects. In the case that a participant experiences a change in medical status or side effects [name], Co-Investigator will be make recommendations regarding continuation in the trial and physician follow-up.
- Since Orlistat may interfere with absorbance of fat-soluble vitamins, all study participants will receive a multivitamin dietary supplement to take daily during the study period.

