AEs are identified through self-report by participants via follow-up phone calls that occur weekly and then are adjusted based on patient's needs and preferences. Participants can request more or less frequent phone calls. Participants will be asked to contact the Emory study staff if additional adverse events occur or if they have any concerns or questions about the protocol.

Any medical condition that is present at the time that the participant is screened will be considered as baseline and not reported as an AE. However, if the study participant's condition deteriorates at any time during the study, it will be recorded as an AE.

Changes in the severity of an AE will be documented to allow an assessment of the duration of the event at each level of severity to be performed. AEs characterized as intermittent require documentation of onset and duration of each episode.

All AEs including local and systemic reactions not meeting the criteria for SAEs will be captured on the appropriate case report form (CRF). Information to be collected includes event description, time of onset, clinician's assessment of severity, relationship to study product (assessed only by those with the training and authority to make a diagnosis), and time of resolution/stabilization of the event. All AEs occurring while on study must be documented appropriately regardless of relationship. All AEs will be followed to adequate resolution

The occurrence of an adverse event (AE) or serious adverse event (SAE) may come to the attention of study personnel during interviews of a study participant presenting for medical care, or upon review by a study monitor.

If participants report gastrointestinal issues following Orlistat use, they will be counseled to reduce the fat content of their meals. If symptoms persist or more serious symptoms arise, participants will be told to discontinue the Orlistat regimen but continue with the diet and exercise plan.

The signs and symptoms of severe liver injury include loss of appetite, itchy skin, yellowing of the skin or the white part of the eyes, amber colored urine, light-colored bowel movements (stools), or pain in the upper right portion of the stomach. People who experience these signs and symptoms should contact their healthcare professional immediately.

Signs and symptoms of pancreatitis include right upper abdominal pain, nausea, vomiting, and loss of appetite.

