Symptoms of kidney problems include swelling, especially of the legs and feet, little or no urine output, frequent or painful urination, blood in the urine, loss of appetite, nausea, vomiting, or severe pain in the back, belly, or groin

An AE will be considered unexpected if the nature, severity, or frequency of the event is not consistent with the risk information previously described for the study intervention. After review of reported symptoms and real-time communication with [name], she will determine the appropriate action needed on a case-by-case basis. If contact with participant is necessary then [name] will learn the identity of the individual, their intervention group and contact information. She will contact the participant to discuss management.

SAE REPORTING

SAEs that are unanticipated, and possibly related to the study intervention will be reported to the, IRB, and NIEHS in accordance with requirements. There are no expected SAEs associated with this trial.

PROCEDURES

Study personnel will record all reportable events with start dates occurring any time after informed consent is obtained until 7 (for non-serious AEs) or 30 days (for SAEs) after the last day of study participation. We will call participants one week and one month after the participant completes the study. Any of these findings detected from one or more of our study assessments found by our study personnel will then follow a chain-of-command in a notification scheme provided to study personnel at the beginning of the study. This chain-of-command will lead to the appropriate channels being notified of a possible event.

After each study telephone call, the staff member will inform the PI, [name] of the occurrence of AE/SAEs since the last visit. If a further input is necessary [name] will request advice from study clinician, [name]. If, after review, there is a confirmation of an AE/SAE, [name], will immediately report to the PI, [name] any serious adverse event, whether or not considered study intervention related, including those listed in the protocol or and must include an assessment of whether there is a reasonable possibility that the study intervention caused the event. [name] will notify patients individually by phone of AEs and SAEs, and study-related results that are of concern and may need additional management by the patient's health care provider.

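### Contacting a participant about an adverse event discloses the treatment group automatically, a wider trigger than the plan's own unblinding rule

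*Combined protocol and SAP*

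**What the plan says.** The Study Design Overview states the design: "A randomized, double-blind, placebo-controlled 6-month trial will be conducted among selected participants from the PBB Registry".

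The Blinding section exempts the two roles that assign and dispense. Of the rest it says: "All other study staff will be blinded to patient medication assignment to ensure no bias occurs in patient data collection and reporting". It repeats the point for the laboratory and the investigator: "All other laboratory and study staff, including the PI will remain blinded". One named person "will be notified of adverse effects reported and will be unblinded whenever necessary for patient safety", and the reader is sent to the Data Safety Monitoring Plan for more.

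That plan contains the AE Management section. There, reported symptoms are reviewed and the clinician settles the action case by case. If contact with the participant is then needed, the clinician "will learn the identity of the individual, their intervention group and contact information", and calls to discuss management.

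Three other places matter:

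- AE Management has the case report form capture a clinician's grading of severity and the "relationship to study product (assessed only by those with the training and authority to make a diagnosis").
- The Procedures part of SAE Reporting requires a causality assessment for serious events.
- Under Protections Against Risk, a co-investigator is to "make recommendations regarding continuation in the trial and physician follow-up" when a participant has side effects or a change in medical status.

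**The concern.** Telephoning a participant takes a name and a number. It does not take the treatment group. AE Management nevertheless releases all three in one step, with no further test of whether the group matters to the problem in hand. If the rule is followed as written, the blind is broken in cases where nothing turns on it.

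Severity, relatedness and advice on continuing are judgements, and judgements are what blinding protects. A clinician who knows the arm may more readily call an event related, or advise stopping, on Orlistat than on placebo. That would distort the adverse-event record and could make stopping of study drug depend on arm for reasons other than the drug's effects. The Blinding section gives freedom from bias in collecting and reporting participant data as its purpose, and adverse-event records are such data.

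**Working it through.** The point rests on no power, variance or sample-size figure, so the check is a comparison of the text.

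**Trigger and content of disclosure**

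| | Blinding section | AE Management |
|---|---|---|
| Trigger | Patient safety makes unblinding necessary | Contact with the participant is necessary |
| Released | Treatment group | Identity, contact details and treatment group together |
| Documented reason or log | None stated | None stated |

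The second trigger is wider than the first: any contact for which the group is irrelevant meets the second and not the first.

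**What comes before and after disclosure.** AE Management places symptom review and the choice of action before the disclosure step. The discussion of management comes after it. Relatedness and severity have no stated place in the sequence. Two consequences follow:

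1. Any advice the clinician gives during the contact is given with the group known.
2. If the same participant has a later event and the same clinician assesses it, the group is already known at that assessment, whatever the order was the first time.

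For the first event itself, the text neither requires nor rules out that attribution is recorded before disclosure.

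**Existing safeguards.** The confidentiality section keeps group-identifying material out of adverse-event reports and annual summaries. This limits onward leakage but does not blind the assessor. The investigator, who may withdraw participants, is to stay blinded, but nothing says that the advice reaching the investigator comes from a blinded source.

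**Route to the weight analysis.** Under Participant Discontinuation or Withdrawal, stopping the drug is not leaving the study, and those who stop are asked to complete the remaining procedures, including the 3- and 6-month blood draws. Weight is measured at those visits. Statistical Modeling specifies intention to treat. Arm-dependent stopping therefore reaches the weight comparison only through reduced exposure to drug, or through people who also leave follow-up.

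**Number of disclosures.** This is 120 × p, where p is the proportion of participants contacted by the clinician about an event. The documents do not give p. Purely as an assumption, p from 0.20 to 0.40 gives 120 × 0.20 = 24 to 120 × 0.40 = 48 assignments disclosed. This counts code breaks and does not measure bias.

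**The case against.** The best defence is that the sections do not conflict. The Blinding section points to the monitoring plan for detail, and a clinician's decision after review that a participant must be called can be read as the working form of a safety need. This has some force, but it does not explain why the group has to travel with the telephone number. A call may be necessary for safety while the group is not.

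The second defence is that the route is filtered. Study staff report to the investigator, the clinician is consulted only if further input is needed, and disclosure follows only if contact is needed. Mild events are by definition those needing no special treatment, and the gastrointestinal rule names neither a clinician call nor an unblinding step. This stands. A reader might infer that every adverse event, even a trivial one, breaks the blind. The documents do not support that, and they give no basis for saying how many contacts there would be or in which arm they would fall.

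The third defence is that adverse events are not endpoints and no between-arm test of them is planned. This also stands. What is exposed is the attribution record and any summary drawn from it, not a specified hypothesis test. Extra stopping on Orlistat with follow-up continued would, moreover, tend to dilute an intention-to-treat weight difference, not create one.

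**Conclusion.** The concern holds in limited form. AE Management states a rule that discloses the group whenever the clinician must contact a participant. That is wider than the Blinding section allows and is not needed to make the contact. It is a stated procedure, not a missing detail, and it should be changed.

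Three stronger readings are tempting but not supported:

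- **That attribution is made unblinded.** No section says so. The action is chosen before disclosure, and the timing of attribution is left open. The supported statement is that nothing prevents unblinded attribution.
- **That one physician does everything.** Names are removed. Treating the person in the Blinding section, the clinician in AE Management, the co-investigator who advises on continuation and the assessors of relatedness as the same individual is plausible but not shown. The difference between the two triggers does not depend on it; the consequences for attribution and continuation advice do, in part.
- **That the primary weight result is biased.** Weight is a measured outcome, the staff who collect data are to be blinded, and follow-up continues after the drug is stopped. Any effect is indirect.

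The size cannot be estimated, because neither the contact rate nor the effect of knowing the arm on the clinician's judgement is given. A low-cost correction is proportionate.

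**What to change.** Reconcile AE Management with the Blinding section:

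1. When contact is needed, release identity and contact details only.
2. Release the treatment group as a separate step, and only when patient safety requires knowing it.
3. Where urgency allows, record severity and relatedness before the group is released. Urgent unblinding must not wait for this.
4. Log each unblinding with date and reason.

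The cost is a revised sentence or two in the protocol, an unblinding log, and a way to show on the case report form that the assessment came before disclosure. The downside is this small amount of extra documentation. Immediate unblinding for safety stays available, and no rule on managing events or stopping study drug has to change.

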Discontinuation from Orlistat does not mean discontinuation from the study, and remaining study procedures should be completed as indicated by the study protocol. If a clinically significant finding is identified (including, but not limited to changes from baseline) after enrollment, [name] will determine if any change in participant management is needed. Any new clinically relevant finding will be reported as an adverse event (AE).

The data to be collected at the time of study intervention discontinuation will include the following:

- Reason for discontinuing
- Participant will be asked to complete all study procedures including 3 month and 6 month blood draws for POPs determination.

The PI may discontinue or withdraw a participant from the study for the following reasons:

- Pregnancy

- Significant study intervention non-compliance
- If any clinical adverse event (AE), laboratory abnormality, or other medical condition or situation occurs such that continued participation in the study would not be in the best interest of the participant
- Disease progression which requires discontinuation of the study intervention
- If the participant meets an exclusion criterion (either newly developed or not previously recognized) that precludes further study participation
- Participant unable to receive Orlistat

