Informed consent is a process that is initiated prior to the individual's agreeing to participate in the study and continues throughout the individual's study participation. Consent forms will be Institutional Review Board (IRB)-approved and the participant will be asked to read and review the document. The investigator or approved team members will explain the research study to the participant and answer any questions that may arise. A verbal explanation will be provided over the phone in terms suited to the participant's comprehension of the purposes, procedures, and potential risks of the study and of their rights as research participants. Participants will have the opportunity to carefully review the consent form and ask questions prior to signing. The participants will also have the opportunity to discuss the study with their family or surrogates or think about it prior to agreeing to participate. The participant will sign the informed consent document prior to any procedures being done specifically for the study. Participants will be informed that participation is voluntary and that they may withdraw from the study at any time, without prejudice. If the participant is unable to save an electronic copy of the consent form, one can be provided via mail. The informed consent process will be conducted and documented in the participant's record, and the form signed electronically, before the participant undergoes any study-specific procedures. The rights and welfare of the participants will be protected.

COMPENSATION

Attrition is a concern for any weight loss intervention; thus, we will use several methods to encourage retention of participants for the duration of the trial. At the beginning of the study we will have frequent telephone contact with participants (at least once/week) followed by reduced frequency as the study

progresses but no less than monthly. These frequent interactions with study participants should encourage retention. We will also contact participants (e-mail or text) to provide encouragement regularly (weekly in months 1-3; at least monthly, but more if needed in months 4-6). Compensation of \$100 per participant will be offered to promote retention over the 6-month duration of the study. Participants will be compensated with \$40 after the first 3 months of participation and an additional \$60 after completion of the 6 months of the trial.

STATISTICAL ANALYSIS

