The statistical hypothesis of interest is whether a mean change in weight or serum levels of POPs is detected at six months from the baseline. $H_0: \delta_I - \delta_P = 0$ vs $H_a: \delta_I - \delta_P > 0$, testing whether the mean change in weight or serum levels of POPs differs (mean change: δ , between the groups; δ_I , intervention group; δ_P , placebo group). The null hypothesis denotes no mean difference between the groups, and the one-sided alternative hypothesis denotes a difference between the groups, with the intervention group having a greater reduction in weight or serum levels of POPs over the course of the trial.

We plan to recruit and screen PBB registry participants, to enroll 120 participants into the trial. Our goal is to have 100 participants complete the 6-month trial duration. These estimates are based on the power analyses described here:

Power Analysis: The primary objective is to determine if the use of Orlistat results in weight loss in this population. Previous studies have shown an average of 2 to 3 kg weight difference between the intervention and placebo groups [16]. Assuming a standard deviation for weight change of 5 kg, we would have adequate power (80%) to detect a 2-3 kg difference ($\alpha=0.05$; $\rho=0.5$) in weight with a sample size of 50 in each group. Power analyses were performed in PASS 13 software [17].

The secondary endpoint is the change in serum concentrations of PBBs, PCBs, DDE, and PBDE at six months from the baseline. For the outcome of change in serum POP levels, we based our sample size estimations on the historical PBB data for PBB registry participants with at least 2 measurements within a year and the pilot data from Jandacek et al [18]. We estimate that the variance of the differences in PBB levels is expected to be between 0.1 and 0.2 log parts per billion (ppb) (σ^2_{diff}). We have used the pooled variances for our power calculations. From our historical data, we expect a 1% reduction in PBB levels due to the natural course of exposure. A sample size of 50 in each group, would provide at least 80% power to detect a mean change in log PBB levels of -0.1 and -0.2 log ppb with a significance level of $\alpha=0.05$.

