- An important medical event based upon appropriate medical judgment of [name]

AEs are graded according to the following scale, based on their impact on the patient:

Mild:

An experience that is transient, and requires no special treatment or intervention. The experience does not generally interfere with usual daily activities. This includes transient laboratory test alterations.

Moderate:

An experience that is alleviated with simple therapeutic treatments. The experience impacts usual daily activities. Includes laboratory test alterations indicating injury, but without long-term risk.

Serious:

An experience that requires therapeutic intervention. The experience interrupts usual daily activities. If hospitalization (or prolongation of hospitalization) is required for treatment, it becomes a serious adverse event.

The study uses the following AE attribution scale to determine the likelihood that they are related to the study intervention:

Not related:

The AE is clearly not related to the study procedures (i.e., another cause of the event is most plausible and/or a clinically plausible temporal sequence is inconsistent with the onset of the event).

Possibly related:

An event that follows a reasonable temporal sequence from the initiation of study procedures, but that could readily have been produced by a number of other factors.

Related:

The AE is clearly related to the study procedures.

AEs are identified through self-report by participants via follow-up phone calls. At the beginning of the study we will have frequent telephone contact with participants (at least once/week) followed by reduced frequency as the study progresses but no less than monthly. Participants can request more frequent phone calls. Participants will be asked to contact the Emory study staff if additional adverse events occur or if they have any concerns or questions about the protocol.

All AEs are reported according to the Emory IRB AE reporting guidelines.

MANAGEMENT OF RISKS TO SUBJECTS

AEs that may be associated with the use Orlistat include:

- Headache
- Oily rectal discharge
- Urgent need to have a bowel movement
- Being unable to control bowel movements
- Oxalate kidney stones/oxalate kidney damage
- Pancreatitis
- Liver injury or failure

AE Management

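### The one-week and one-month safety calls are timed from completing the study, so participants who leave the study early have no scheduled call in the 7- and 30-day event window

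*Combined protocol and SAP*

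**What the plan says.** Two adjacent sentences in the Procedures text under SAE Reporting set the recording window and the calls.

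- **Window.** Reportable events are recorded from informed consent "until 7 (for non-serious AEs) or 30 days (for SAEs) after the last day of study participation". Nothing limits this to participants who finish.
- **Calls.** "We will call participants one week and one month after the participant completes the study".

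The last row of Figure 2 (Schedule of Activities), for the post-study telephone calls, reads "One week and one month after completion". Figure 2 has no row or column for early withdrawal.

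On how events are found, Collection and Reporting of SAEs and AEs says "AEs are identified through self-report by participants via follow-up phone calls". Figure 2 lists the routine calls for months 1 to 6.

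**The concern.** The window is anchored to the end of participation, whatever the reason for it. The calls are anchored to completion. The two coincide for a participant who finishes six months and separate for one who leaves sooner. Because telephone contact is the plan's main way of finding events, a participant with no scheduled call has no prompted ascertainment in a period the plan says it will cover.

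The protocol names kidney, pancreatic and liver injury as the serious risks of the drug. The clinical blood tests are repeated only at month 6, and no exit test is specified for someone who leaves the study before then. For these participants a call would be the main remaining prompt for a new event. At stake is how complete the safety record is for early leavers.

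**Working it through.** The plan states no figure for this point, so there is none to reproduce. The check compares the passages and then counts the participants affected.

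**1. What completing means.** The term is not formally defined, so its use elsewhere is the best guide. Statistical Analysis: "Our goal is to have 100 participants complete the 6-month trial duration". Compensation: "an additional \$60 after completion of the 6 months of the trial". The Study Population entry in the Study Overview uses the word in the same way. In all three places it means finishing six months.

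**2. Do the calls match the window?**

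| Participant | Window | Scheduled calls in the window |
|---|---|---|
| Finishes 6 months | 7 days (non-serious), 30 days (serious) | 2 of 2: one week, one month |
| Stops capsules, stays in study, finishes | Same | 2 of 2 |
| Leaves or is withdrawn from the study early | Same | 0 of 2 specified |

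**3. Does another section supply the call?**

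- Participant Discontinuation or Withdrawal requires the reason to be recorded on a case report form. It also requires attempts to regain contact after a missed 3- or 6-month blood draw. Those attempts are not safety calls timed from exit.
- AE Management follows reported events until they resolve. That covers known events and does not search for new ones.
- Participants are asked to contact staff about further events, which is unprompted.

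No section schedules a call 7 or 30 days after an early exit.

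**4. Who can be in the third row.** Besides those who leave by choice, "The PI may discontinue or withdraw a participant from the study for the following reasons". The list includes an adverse event, a laboratory abnormality, a newly met exclusion criterion and pregnancy. Participants withdrawn this way have not necessarily withdrawn consent, and many could be telephoned.

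**5. How many.**

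- Enrolled minus completing: 120 − 100 = 20, and 20/120 = 16.7%.
- At the stated 20% attrition: 0.20 × 120 = 24.

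The two differ because the plan reaches 60 per arm as 50 × 1.20, and losing 10 of 60 is 16.7%. The difference does not matter here. Both counts are upper limits, because attrition may include missing data without study exit and people randomised but never dosed.

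**6. Calls needed to close the gap.** 2 × 20 = 40 to 2 × 24 = 48, at most.

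**The case against.** The strongest reply is that the call sentence directly follows the window sentence and its intervals match the window, so the calls may be meant to serve it for everyone. That reading is possible, since the protocol never says that calls are confined to completers. But it conflicts with how the protocol uses the word elsewhere, and staff working from Figure 2 would have no prompt to call a leaver. If the sponsor does intend to call everyone, the edit simply records that.

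Three stronger readings are tempting, and the documents do not support them.

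- **A reader might infer that the participants at highest risk are the ones not called.** The protocol says "Discontinuation from Orlistat does not mean discontinuation from the study". AE Management tells those with persistent or more serious symptoms to stop the drug and continue the diet and exercise plan. By default they keep their calls, at least monthly, and get the post-study calls if they finish. Withdrawal from the study for an adverse event is at the investigator's discretion.
- **A reader might infer that later events would surface only if the participant telephoned.** Reported events are followed until they resolve, so progression of a known event would be seen. AE Management also allows for detection when a participant presents for medical care or on review by a study monitor. What remains is new events with no prompted enquiry.
- **A reader might infer that the comparison of arms is biased towards the drug looking safer.** Statistical Analysis specifies no comparison of adverse events between arms, and the documents do not say how early exits will divide between arms. If they divide evenly, there is no differential ascertainment from this source.

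**Conclusion.** The point holds in limited form. The plan commits to recording events for 7 and 30 days after participation ends, but schedules calls in that period only for participants who complete. This rests on reading completion as finishing six months, which the protocol's own usage supports although it gives no definition.

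The affected group is those who leave the study, at most about 20 to 24 of 120. The part that can be remedied is smaller, because some will decline contact or be unreachable. The direction and size of any imbalance between arms cannot be stated from the documents. Sample size, power and the efficacy analysis are unaffected. This is a modest gap in safety ascertainment that is cheap to close.

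**What to change.** Reconcile the call trigger with the recording window in two places: the Procedures text under SAE Reporting and the last row of Figure 2. In both, time the one-week and one-month calls from the last day of study participation. State that they apply to every randomised participant who took study capsules, including those who withdraw or are withdrawn early, unless they decline contact.

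The cost is two wording edits and at most about 40 to 48 short calls by existing staff. The actual number will be lower where leavers decline or cannot be reached. No dose, stopping rule or analysis changes.
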